Participants who meet study inclusion criteria and consent to participate will be stratified by orthopaedic surgeon and randomized in permuted blocks of 3, one to each study group, to ensure that patients from each participating physician and site have an equal chance of being randomized to one of the 3 groups. Given that we will have 30 orthopaedic surgeons participating in the study (see Table 5 below), this approach will control for temporal and clustering effects resulting from single surgeons having imbalances in the numbers of patients in each treatment group over time. Assignment to one of the 3 groups will be accomplished with a computer generated table of random numbers created by the biostatistician and provided to the study coordinators at each site via a secure website. After collecting baseline data, each site's study coordinator will conduct treatment allocation by use of the study web site, allowing the treating surgeon and the follow-up data collectors (site coordinators and research assistants) to be blinded. We will instruct all surgeons of the importance of avoiding study contamination by not querying patients about study interventions. Surgeons also will be asked to report if they became aware of group assignment during the study. These data will be tracked and reported at the end of the study.

All data collected at each site will be obtained by data collectors who are blinded to group allocation. This will be accomplished by assigning patients to one of the three treatment groups using a secure website and then providing patients with treatment allocation information in random number matched pre-sealed opaque envelopes. Patients will be instructed to open envelopes once they return home and they will be asked not to mention their group assignment to the data collectors. Information in the envelopes will inform patients about group assignment and will instruct patients to contact site PIs if they have any questions about the treatment to which they have been assigned. Because site PIs will not be collecting data from patients, we will optimize the likelihood of keeping data collectors blinded to group allocation during the course of study.

Interventions

Pain Coping Skills Training

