Patients assigned to pain coping skills training will have 8 sessions delivered by one of the sites clinical psychologists with experience treating patients with pain. There will be an initial in-person session approximately 1 month prior to surgery, six weekly telephone-based sessions with three prior to surgery and three during the 3 weeks following surgery, and one final in-person session approximately 1 month following surgery. Eight skills training sessions delivered over a 2 month period has been shown to be effective in several behavioral trials.⁴⁴⁻⁵⁰ Use of telephone-based sessions is a new development in behavioral research and one which we have prior experience. It offers a cost-effective and practical approach for patients who have difficulty with mobility and travel.^{61,62}

The pain coping skills training intervention was developed as part of our R34 funding and is based on information gathered in previous studies of chronic and arthritic pain by [name], [name] and others,^{45,54,55,63-68} as well as our pilot study.⁶⁹ The intervention is designed to modify coping strategies found to be related to pain and disability (please see the clinician training manual and the corresponding patient manual in the MOOP). The final protocol was based upon an extensive review of the literature, intensive discussions among the investigators, input from international experts working in the field of psychosocial interventions and pain catastrophizing, and our clinical experience working with OA patients who are high catastrophizers. There was consensus among all involved on three points: (1) that an overly narrow protocol, i.e. a simple attempt to use cognitive restructuring to alter catastrophizing only was unlikely to work because it would not examine the broader context in which catastrophizing cognitions occur for these patients; (2) that the CST protocol should not be as broad in scope or as intensive as comprehensive cognitive-behavioral therapy (CBT) interventions for pain; and (3) that CST should be used since it is the only intervention to date that has been shown in controlled studies to reduce both pain catastrophizing and pain.

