Enhancing Maintenance	Relapse Prevention Training

Use of clinical

psychologists to deliver the skills training may limit generalizability of our findings to settings with adequately trained psychologists. Because evidence is lacking on the use of lesser trained practitioners and because, in our experience, this patient population is particularly challenging given their higher levels of pain catastrophizing, we believe it is important to test the intervention using practitioners with advanced skills. However, we will plan implementation studies with non-psychologist practitioners if the results indicate that the intervention is effective.

Arthritis Education Comparison Condition

Patients randomly assigned to Arthritis Education, a comparison condition that will control for participation in a trial, time and therapist attention, will receive detailed educational information from a nurse educator about OA and its treatment. Nurse educators have similar levels of clinical experience as clinical psychologists, which will assist in making the argument that it is the content of the interventions and not the delivery of these interventions that we will be testing in the trial. The arthritis education sessions will use a presentation and discussion format similar to that originally described by Lorig for arthritis education.⁷⁸⁻⁸⁰ The clinician and patient manuals were developed as part of our R34 funding (see MOOP). Figures and discussion sessions will present information on the nature of arthritis, what to expect following knee arthroplasty, treatment of osteoarthritis, the role of exercise, joint protection and making future treatment decisions.

This general approach to an arthritis education comparison condition has been used successfully in many behavioral studies and in several trials conducted by [name] and [name].^{44-50,55} Use of an education comparison condition enhances the scientific credibility of the study by testing whether the "pain coping" component of the experimental intervention effectively reduces pain and improves function over that seen in patients who receive a similar dose of time and attention from a health professional, but no specific pain coping skills.

Usual Care

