effect of 2 WOMAC Pain points for coping skills training for three reasons. First, our pilot study used a quasi-experimental design which may overestimate treatment effects because of non-randomization. Second, estimates were based on comparisons to usual care, and we suspect that some therapeutic benefit will be experienced by the arthritis education group. Third, these data represent only short-term changes following surgery and most patients continue to improve up to a year following surgery.^{9,14}

Using a two-sided two group 0.05-level t-test of differences in means and assuming the intervention difference minus the arthritis education control difference is at least 2.0 WOMAC Pain points, a sample size of 107 in each group will have 91% power to detect this difference, assuming that the common standard deviation is 4.34 (based on pilot work described earlier). This corresponds to an effect size of 0.46 which is consistent with the effect of other behavioral interventions for knee arthritis.¹²⁷⁻¹²⁹ This sample size also adequately powers the study to detect a 20% difference between groups in the number of patients with a 50% or greater improvements in WOMAC pain relative to baseline scores.^{9,10,12-15,130} This effect will be equivalent to an odds ratio of 2.25 and is equivalent to a Numbers Needed to Treat (NNT) of 5 which is indicative of an effective intervention.¹³¹ The revised CONSORT statement endorses use of indexes such as number needed to treat.¹³²

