Thus, the total required sample size is 321 (107 patients per arm) for the planned 3-arm trial. Based on our pilot study, we expect 5% attrition due to early drop-out resulting from cancelled surgery. Patients who undergo surgery and drop out due to lack of interest, unrelated medical illness or loss of follow-up also will be included in the intent to treat analysis. Our pilot study of 18 patients suggests this number will be on the order of 10%, although this estimate is likely to be low because the pilot study was only 2 months in duration. Our previous work with similar types of patients suggests that loss to follow-up will likely be closer to 20% one year following surgery.^{14,29} Therefore, 402 patients (134 patients per study arm) will need to be enrolled in the trial (321+64 due to loss of follow-up+17 due to cancelled surgery). A total of 2,100 patients will need to be screened because our pilot studies indicated that approximately 19% of the screened sample will actually participate (ie. they will meet all inclusion and exclusion criteria AND provide consent for the study). Stratification by surgeon and by site is expected to reduce outcome variability and thereby increase power.

Data Analysis

Intention to treat (ITT) will be the primary approach for all analyses and, depending on the pattern of missing data (missing at random, completely at random or not missing at random), multiple imputation using SAS StAT/MI methods will be used to impute values for those lost to follow-up.¹³³ In addition, we will compare the ITT analysis to the results for patients who actually undergo surgery to determine if undergoing surgery affects the findings. For the primary analysis, the effect of treatment will be assessed using linear mixed models with time as a repeated factor. The model will account for correlation over time within participants, correlations within clinics, surgeons, and baseline covariates. Surgical approach, complications, medication and physical therapy use will be assessed for potential effects.

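### The primary model and the power calculation leave out clustering by psychologist and nurse educator; if outcomes vary by provider at all, both primary contrasts get standard errors that are too small, coping skills vs education more so

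*Combined protocol and SAP*

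**What the plan says.** Under Data Analysis, the primary analysis is a linear mixed model with time as a repeated factor. Its correlation structure is given in one sentence: "The model will account for correlation over time within participants, correlations within clinics, surgeons, and baseline covariates". No psychologist or nurse-educator term appears there or elsewhere in the document.

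Under Interventions, coping-skills patients have "8 sessions delivered by one of the sites clinical psychologists with experience treating patients with pain". Under Arthritis Education Comparison Condition, patients "will receive detailed educational information from a nurse educator about OA and its treatment". Under Usual Care, patients have no study provider. The document names four sites but does not say how many psychologists or nurse educators each will have.

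Under Sample Size Estimations, the calculation is introduced as follows: "Using a two-sided two group 0.05-level t-test of differences in means". It supposes that "the intervention difference minus the arthritis education control difference is at least 2.0 WOMAC Pain points", "assuming that the common standard deviation is 4.34", and concludes that "a sample size of 107 in each group will have 91% power to detect this difference". It includes no ICC or design effect. That section's only remark linking site and surgeon to power is that stratification should raise it.

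Under Randomization and Blinding, patients are stratified by surgeon and "randomized in permuted blocks of 3, one to each study group".

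**The concern.** Patients who share a psychologist may do better or worse together, and likewise patients who share a nurse educator. These providers are nested within arm: a psychologist treats only coping-skills patients and a nurse educator only education patients. Any difference between providers therefore feeds directly into the treatment contrast.

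The terms that the plan does include work differently. Blocks of three within surgeon spread each surgeon's patients, and so each clinic's, evenly over the three arms. A clinic or surgeon effect then moves all arms together and largely cancels from the contrasts. It cannot absorb an effect present in one arm only.

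At stake are the error rate and interval width for hypotheses 1a and 1b, and whether the stated power describes this design. The plan takes trouble over clustering by surgeon, who does not deliver the study interventions, but makes no matching provision for those who do.

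**Working it through.** **Inputs from the document (Sample Size Estimations):** n = 107 per arm, difference d = 2.0, SD = 4.34, two-sided alpha 0.05.

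**Assumptions (not in the document):** k = 4 or 8 providers per treated arm, that is, one or two per site; provider ICC from 0 to 0.05.

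**Step 1. Reproduce the plan's figure.** The standard error is 4.34 × √(2/107) = 0.593, and 2.0/0.593 = 3.37. Power = Φ(3.37 − 1.96) = 92.1%; the exact t-test with 212 df gives 91.9%. The stated 91% is reproduced to within about one point.

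**Step 2. Formulas.**
- Design effect in a treated arm: DE = 1 + (107/k − 1) × ICC.
- Variance factor F: DE for coping skills vs education (both arms clustered); (DE + 1)/2 for coping skills vs usual care (one arm clustered).
- True type I error of a nominal 5% test that ignores providers: P(|Z| > 1.96/√F).
- Power when the standard error is correct: Φ(3.37/√F − 1.96).

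Example, k = 4 and ICC 0.05: DE = 1 + (26.75 − 1) × 0.05 = 2.29. Against education, √F = 1.51, type I error is 19.5%, and power is Φ(3.37/1.51 − 1.96) = 61%. Against usual care, F = (2.29 + 1)/2 = 1.64, √F = 1.28, and type I error is 12.6%.

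**Step 3. Results.** The document states power only for the education contrast. The usual-care power below applies the same d and SD to that contrast.

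| k | ICC | DE | Type I, vs education | Type I, vs usual care | Power, vs education | Power, vs usual care |
|---|---|---|---|---|---|---|
| any | 0 | 1.00 | 5.0% | 5.0% | 92.1% | 92.1% |
| 8 | 0.01 | 1.12 | 6.4% | 5.7% | 88.9% | 90.5% |
| 8 | 0.02 | 1.25 | 7.9% | 6.4% | 85.5% | 88.9% |
| 8 | 0.05 | 1.62 | 12.3% | 8.7% | 75.5% | 83.8% |
| 4 | 0.01 | 1.26 | 8.0% | 6.5% | 85.2% | 88.7% |
| 4 | 0.02 | 1.52 | 11.1% | 8.0% | 78.2% | 85.2% |
| 4 | 0.05 | 2.29 | 19.5% | 12.6% | 60.6% | 74.8% |

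**Step 4. Does the clinic term absorb the provider effect?** A simulation used 4 sites, one provider per arm per site, a site effect in the fitted model, no provider term, and 4,000 runs per setting. Type I error at ICC 0 / 0.01 / 0.02 / 0.05 was 4.8% / 7.1% / 11.7% / 18.8% against education and 5.9% / 6.0% / 8.4% / 13.0% against usual care. These agree with the formulas apart from simulation noise, so the clinic term does not help.

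**Step 5. Degrees of freedom.** The power figures in Step 3 use the normal distribution. A test that treats providers as the units has 2(k − 1) df against education. With k = 4 (6 df), power is 80% at ICC 0 and 71% / 63% / 46% at ICC 0.01 / 0.02 / 0.05. With k = 8 (14 df), it is 88% at ICC 0 and 84% / 80% / 69%.

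**The case against.** The strongest reply is that the harm is conditional. A reader might infer that the standard errors are certainly too small and that 91% is certainly too high. The documents do not support that: at ICC 0 nothing changes, and they supply neither an ICC nor a provider count.

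There are reasons to expect a small ICC. Sessions end about one month after surgery, while the endpoint is at one year. The section on treatment fidelity specifies manuals, common training, taping of all sessions, supervision, remedial training, and adherence and competence thresholds. These steps may shrink provider variation, but nothing shows that they remove it, and the analysis has no safeguard if they do not.

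The type I error figures also need a particular null: providers differ in effect while the average effect is zero. If neither intervention changes one-year pain for anyone, providers have no effect to differ in and the test keeps its size. Conditioning on the trial's own providers is a possible inference target too. Both points are fair. However, intervals that are too narrow do not depend on the null: at k = 4 and ICC 0.05, a nominal 95% interval against education covers about 80%. The plan also discusses applying its findings in settings with adequately trained psychologists, which reaches beyond the providers in the trial.

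On power, the t-test takes no credit for baseline covariates or stratification. At k = 4 and ICC 0.01, covariates explaining about 26% of the within-provider variance would cancel the loss: (1 − R²) × 0.99/107 + 0.01/4 = 1/107 gives R² = 0.26. At k = 4 and ICC 0.05 none could, because the provider part alone (0.05/4 = 0.0125) exceeds 1/107 = 0.0093. A net overstatement of power is therefore possible but not proven. Covariates that explain variation within providers do not repair the type I error.

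Finally, the reference to correlation within clinics is brief. A clinic-by-arm term would pick up provider effects if each site had one provider per arm, but the plan does not state one.

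**Conclusion.** The omission is real in both the model and the sample size calculation, and the listed clinic and surgeon terms do not cover it. Its consequence is conditional on a provider ICC above 0. Over an assumed ICC of 0 to 0.05 with 4 to 8 providers per arm, type I error is 5% to about 20% against education and 5% to about 13% against usual care. Normal-approximation power against education is 92% down to 61%, before covariate gains.

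The two contrasts should not be treated alike. Usual care has no study provider, so hypothesis 1b is affected less than 1a, and the 91% is stated only for the education contrast. The ICC range and the provider counts are the review's assumptions. This should be settled before analysis, because adding or dropping a provider term after the data are seen would look selective.

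**What to change.** - **Data.** Record the psychologist or nurse educator for each treated patient. The plan mentions on-line documentation of delivery and tracking of clinician visits, from which a reader might infer that provider identity is already held. No passage says so, and the sponsor should confirm it. State the number of providers per site.
- **Model.** Prespecify a partially nested mixed model with separate provider random effects in the coping-skills and education arms, usual-care patients as singletons, and a small-sample correction such as Kenward-Roger. Report it beside the model without the term. Make it the primary model or, at minimum, a prespecified sensitivity analysis. Report the provider ICC.
- **Power.** Present the 91% as the value at ICC 0 without a provider term, with a range up to ICC 0.05.

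**Cost.** Intervals will be wider and the stated power less favourable. With only about 4 providers per arm, the variance component is poorly estimated and df are few; power against education is then roughly 71% to 46% at ICC 0.01 to 0.05. That is a fair argument for the sensitivity-analysis option if providers prove to be few. No extra patients or visits are needed. If provider identity is confirmed as captured, the change is to the analysis text only; otherwise one data field is added.

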Specific Aim 1. To assess the efficacy of pain coping skills training in reducing knee pain and improving function. Our two primary hypotheses (to be tested in the clinical trial) are the following:

- **Hypothesis 1a.** Pain coping skills training is more effective than arthritis care education in *decreasing knee pain during functional activities*.
- **Hypothesis 1b.** Pain coping skills training is more effective than usual care in *decreasing knee pain during functional activities*.

We also will examine **one secondary (hyp. 2) and one tertiary (hyp. 3) hypothesis**.

- **Hypothesis 2.** Pain coping skills training is more effective than arthritis education or usual care in improving self-reported function, physical performance, pain intensity, pain catastrophizing, and patient global ratings of improvement.
- **Hypothesis 3.** Pain coping skills training will reduce direct medical costs and indirect (i.e. patient time) costs relative to arthritis care education and usual care. When accounting for costs associated with pain coping skills training, the intervention will be cost saving or cost-effective relative to arthritis care education and usual care as measured by the incremental cost per quality-adjusted life-year.

Specific Aim 2. To determine if treatment benefits of pain coping skills are mediated by changes in pain catastrophizing:

- **Hypothesis 4.** Changes in pain catastrophizing that occur over the course of pain coping skills training will mediate treatment-related improvements in pain and self-reported function during recovery.
-

Research Strategy

Significance: Specific Aim 1

Knee arthroplasty surgery (TKA) is a common and generally effective procedure.¹ For example, projections estimate that 3.5 million procedures will be conducted annually by 2030.² Cost data for TKA also are impressive. Mean procedural charges per patient in 2003, reported in 2005 dollars, were \$38,000 per primary surgery and \$48,000 per revision surgery.³ If these procedural charges data were extrapolated to the 2010 volume data projections, procedural charges would total approximately \$28 billion dollars annually.

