The three major sources of treatment variation in knee arthroplasty are surgical technique, physical therapy and medication usage. A variety of surgical approaches and implants are available with no clear evidence of superiority among the options.⁵⁶ Surgeons are accustomed to conducting this surgery, for the most part, in the way that they were trained and to attempt to enforce standardization in surgical procedures was, in our view, unrealistic. In lieu of controls for surgical approach we will: (1) randomly stratify by surgeon and, (2) collect data from each surgeon on: (a) type of implant (i.e., cruciate retaining, posterior stabilized, rotating platform, patellar resurfacing (yes or no for each); (b) surgical approach (mid-vastus, sub vastus, medial parapetallar); and (c) use of cement (yes or no). These data will be collected for all patients and examined as potential covariates. Because surgical approach will not be standardized, there is no concern for a lack of equipoise among participating surgeons. Physical therapy for patients following TKR, in contrast, is generally similar across clinics in that the goal of physical therapy is to enhance functional status via range-of-motion and strengthening exercise and gait and balance training. There is no evidence of a clear benefit of any single physical therapy approach at one year.⁵⁷ To account for the duration (dosage) of physical therapy we will collect data on the total number of physical therapy visits for all patients and assess the impact of number of visits on outcome. Regarding medication use, we will track medication use in all three arms with a comprehensive medication list (see MOOP) to categorize the medication profile for each patient over the course of the study.

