Chart abstractors blinded to treatment assignment will indicate if the patient had one or more of the following post-surgical complications: implant infection requiring surgery, implant failure requiring revision, implant loosening requiring revision, symptomatic DVT or PE, patellar dislocation or failure and knee fibrosis requiring manipulation. These complications typically require hospitalization or additional care and may influence outcome independent of the interventions being studied. Randomization will likely control for these effects, but we also will statistically adjust for the impact of these complications on study findings, if necessary. Overall, this pragmatic approach will, in our view enhance study generalizability.

Inclusion criteria will be the following:

- Adults 18 years of age or older and capable of providing informed consent.
- Diagnosis of osteoarthritis using American College of Rheumatology (ACR) criteria of moderate to severe knee OA⁵⁸ and function limiting pain as determined by the patients' orthopaedic surgeons.
- Scheduled for an elective unilateral total knee arthroplasty no sooner than 2 weeks or later than 8 weeks from the time of recruitment.
- Score of ≥ 16 on the Pain Catastrophizing Scale and ≥ 5 on the WOMAC Pain scale.
- Able to read and speak English.

Exclusion criteria will be the following:

- Scheduled for revision arthroplasty surgery.
 - Unable to or declines consent for study participation.
-

- Self-reported diagnosis of inflammatory arthritis (i.e. rheumatoid arthritis, psoriatic arthritis, systemic lupus erythematosus, ankylosing spondylitis).
- Arthroplasty scheduled because of a fracture, malignancy or an infection.
- Scheduled for bilateral arthroplasty surgery.
- Scheduled for unicompartmental arthroplasty.
- Self reported plan to undergo hip or knee arthroplasty within one year after current knee arthroplasty.
- Presence of severe depression (20 or higher) using the PHQ-8 depression screener.^{59,60}

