Because the standard of care in joint arthroplasty includes no treatment directed toward poor pain coping, we have added a "usual care" group to determine real world effects of pain coping skills. Patients in the usual care group will only receive care that they would have routinely received had they not been entered in the study.

Economic Evaluation

Four types of information will be collected throughout the study for use in the economic evaluation: (1) all-cause medical resource use; (2) patient time; (3) health utilities; and (4) resources required to provide the coping skills training, arthritis education and usual care. We will collect information on all-cause medical resource use including hospitalizations, emergency department and urgent care visits, orthopedic-related procedures, medications for pain and/or inflammation, and outpatient visits, including sessions for physical and occupational therapy. This information will be ascertained via patient self-report and supplemented with medical records abstraction. To improve the accuracy of patient self-report, patient diaries will be designed to track medical resource use to record their estimates of time spent receiving the interventions, adhering to treatment recommendations (e.g. physical therapy), and employing coping skills.⁸¹ Validity of patient diaries of medical service utilization is generally supported, particularly when instructions to patients are clear.^{82,83} To incorporate potential differences in health-related quality of life experienced by patients in the three study arms into the cost-effectiveness analysis, we will measure health utilities using the 5-level EQ-5D (5L EQ-5D).⁸⁴ According to the EuroQoL group, preference weights for the 5L EQ-5D should be available by the end of 2012 (EuroQol Group Executive Office - personal communication). Finally, we will prospectively collect information on time spent by clinical psychologists and nurse educators and other individuals involved with the delivery of the study interventions as a basis for estimating intervention costs.

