Estimates of the effect of pain coping skills training will be obtained by constructing linear contrasts to compare the mean change in outcome from baseline to each of the key time points (2 months, 6 months and 1 year) between the pain coping skills group and the two control groups, with adjustment for the other variables. Analyses of the secondary outcome variables will be conducted using a similar approach. For the analyses using dichotomous outcomes of $\geq 50\%$ improvement at 6 months and 12 months, generalized linear models with logistic regression will be used to compare the proportion of patients with $\geq 50\%$ improvement after adjustment for baseline data.

Our study is powered to detect clinically important differences in WOMAC Pain scores among treatment groups. As an additional secondary analysis, we also will examine the effects of potential moderators. Moderators are baseline characteristics that predict treatment effects.¹³⁴ Additional psychosocial issues may influence treatment effects in knee arthroplasty patients with high levels of pain catastrophizing. Potential

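### Medication use, physical-therapy visits and complications, all arising after randomisation, are not kept out of the model behind the primary WOMAC Pain contrasts

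*Combined protocol and SAP*

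**What the plan says.** All references are to the combined protocol and SAP.

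- **Data Analysis, first paragraph.** Intention to treat is the main approach for every analysis. The primary model is a linear mixed model with time as a repeated factor. It allows for correlation within participants, clinics and surgeons, and for baseline covariates. The next sentence reads "Surgical approach, complications, medication and physical therapy use will be assessed for potential effects".
- **Data Analysis, second paragraph.** Mean changes from baseline to 2 months, 6 months and 1 year are compared "between the pain coping skills group and the two control groups, with adjustment for the other variables". Secondary outcomes follow a similar approach. The responder analysis (at least 50% improvement), by contrast, is adjusted for baseline data.
- **Participants, on sources of treatment variation.** To account for the dose of physical therapy, the team will "collect data on the total number of physical therapy visits for all patients and assess the impact of number of visits on outcome". Medication is tracked in all three arms through the study to build a profile for each patient.
- **Participants, on post-surgical complications.** Randomisation is expected to balance these, but "we also will statistically adjust for the impact of these complications on study findings, if necessary".
- **Hypothesis 3.** "Pain coping skills training will reduce direct medical costs and indirect (i.e. patient time) costs relative to arthritis care education and usual care".
- **Economic Evaluation.** The resource use to be collected includes "medications for pain and/or inflammation, and outpatient visits, including sessions for physical and occupational therapy".

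**The concern.** Hypotheses 1a and 1b ask whether being assigned to coping skills training lowers knee pain more than arthritis education or usual care. Randomisation supports that comparison only if the model conditions on things that assignment cannot change. Analgesic use and therapy attendance do not meet that condition. Patients who cope better may use less of both, and patients in more pain may use more of both. A contrast that holds them equal answers a different question from the hypotheses.

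A second problem is freedom of choice. The contrasts adjust for an undefined set, and complications are adjusted for when judged necessary. Two analysts following the text could therefore report different 1-year effects from the same data, and the choice could be made with outcomes in view. Because the secondary outcomes use a similar approach, the ambiguity carries over to them.

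**Working it through.** **1. Timing.** Randomization and Blinding places allocation after baseline data collection. Under Pain Coping Skills Training, the first in-person session and three of the six telephone sessions come before surgery, so 1 + 3 = 4 of the 8 sessions are pre-operative. Then:
- therapy visits are counted over the period after surgery;
- medication is recorded throughout the study;
- the listed complications are post-surgical.

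All three arise after randomisation, and after treatment is due to have begun. Surgical approach, named in the same sentence, is also recorded at surgery. It is, however, the choice of a surgeon whom the plan keeps blinded, and this point does not rest on it.

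**2. What the text permits.** The description of the model names baseline covariates. The following sentence brings in the later variables. The contrasts then adjust for an unnamed set. No section gives an entry rule, limits the primary contrast to baseline variables, or makes a model with later variables supportive. The baseline-only wording does appear in the same paragraph, but only for the responder analysis.

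**3. Link to the intervention.** Hypothesis 3 expects lower direct medical and patient-time costs. Economic Evaluation counts pain medication and therapy sessions within the resource use behind those costs. These measures are thus components of a hypothesised outcome and also candidates for adjustment of the primary contrast.

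**4. The plan's own figure.** Sample Size Estimations works from these inputs: "Using a two-sided two group 0.05-level t-test of differences in means", "assuming the intervention difference minus the arthritis education control difference is at least 2.0 WOMAC Pain points", SD 4.34 and 107 per arm.
- Effect size: 2.0 / 4.34 = 0.46, as stated.
- Normal approximation: 2.0 / (4.34 × √(2/107)) = 3.37, and Φ(3.37 − 1.96) = 92.1%.
- Noncentral t with 212 degrees of freedom: 91.9%.

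The stated 91% is reproduced to within about one point. It refers to an unadjusted difference between arms, that is, to the total effect of assignment.

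**5. Direction of bias.** Take a simple single-time-point model. Let assignment shift use by *a* SD, and let one SD of use go with *b* points of pain within arm. Then

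adjusted effect = total effect − *a* × *b*.

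With a total effect of −2.0 and an assumed shift *a* = −0.2:
- *b* = +2 (use marks pain): −2.0 − (−0.2 × 2) = −1.6, an understatement;
- *b* = −1 (use relieves pain): −2.0 − (−0.2 × −1) = −2.2, an overstatement.

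The values of *a* and *b* are assumptions chosen only to show that both signs can occur. The documents give neither.

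**6. Dependence on model form.** The plan's contrasts are of change from baseline in a repeated-measures model. If baseline is one of the repeated measurements, a patient-level covariate *C* that is fixed over time and enters as a main effect adds γ*C* to both the baseline and the 1-year value. With complete data it cancels: (Y₁ + γ*C*) − (Y₀ + γ*C*) = Y₁ − Y₀. Bias then needs a covariate-by-time term, a time-varying covariate (possible for medication), or a change-score or ANCOVA form. The plan does not say which applies.

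**The case against.** The strongest reply is that the plan never commits to this adjustment. The model sentence names baseline covariates only, and assessing variables for potential effects need not mean putting them in the primary model. The unnamed variables in the contrast sentence may simply be those of the model just described, and intention to treat governs throughout. This is a fair reading, and it rules out saying that the sponsor will adjust for these variables. It does not remove the ambiguity: the contrast sentence lacks the baseline limit that the responder analysis has, and the complications sentence does state an intention to adjust.

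Three further objections stand and limit the point.

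- A reader might infer that Hypothesis 3 predicts less medication and therapy use. It predicts lower costs and names neither. The resource list also covers hospital stays, emergency visits and procedures, so costs could fall while analgesic and therapy use did not.
- A reader might treat complications as part of the same causal path. The Participants section says that they may influence outcome independently of the interventions, has them abstracted by blinded staff, and expects randomisation to control for them. What remains there is mainly the missing criterion.
- A reader might infer that the adjusted analysis would lose part of a true benefit and much of its power. Steps 5 and 6 of the working show that neither the sign nor the presence of bias is fixed by the documents.

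**Conclusion.** The point holds as a defect of specification. The plan leaves room for variables arising after randomisation to enter the model that yields the primary WOMAC Pain contrasts, with no list, rule or label to prevent it. If medication or therapy use entered in a form that does not cancel, the estimate could differ from the effect of assignment in either direction. For complications the case rests chiefly on the open-ended proviso.

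No size is attached. The documents give neither the effect of the intervention on use, nor the relation of use to 1-year pain, nor the form in which the covariates would enter. A power-loss figure would rest wholly on assumed values. The sample size is unaffected: with these variables kept out, the 2.0-point target and the stated 91% power stand.

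**What to change.** 1. **Data Analysis, contrast sentence.** Replace the unnamed variables with a list fixed before randomisation: baseline WOMAC Pain, surgeon, site and named baseline covariates. Apply it to the primary and the secondary contrasts.
2. **Data Analysis, sentence on potential effects.** State that models containing medication use, therapy visits or complications are labelled supportive analyses and do not define the treatment effect.
3. **Participants, complications.** Replace the whole adjustment clause with reporting of complications by arm and a supportive adjusted analysis. Striking only the closing proviso would make matters worse, because it would leave an unconditional commitment to adjust.

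The change is to wording only, with no new data and no change in sample size. The cost is that any outcome variance explained by these variables is not used in the primary model.
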